8.2.4.1. Overview of Planned Adverse Event Analyses

Table 10 provides an overview of the planned adverse event safety analyses.

Table 10 Overview of Planned Adverse Event Safety Analyses

Parameter	Absolute			
	Summary		Individual	
	T	F	F	L
AESIs & PhRMA SPERT Adverse Event Analyses				
Analysis of AESIs	Y	Y		
Analysis of Common ($\geq 5\%$) AEs	Y	Y		
Adverse Events				
All AEs by System Organ Class (SOC) and Preferred Term	Y			Y
All AEs by System Organ Class (SOC) and Preferred Term (subjects and occurrences)	Y			
All AEs by SOC and Preferred Term by Subgroups	Y			
All AEs by Overall Frequency	Y			
Common AEs by Overall Frequency	Y	Y ¹		
All AEs by Maximum Intensity	Y			
All Drug-Related AEs by Maximum Intensity	Y			
All Drug-Related AEs by SOC and Preferred Term	Y			
Common Non-Serious AEs by SOC and Preferred Term (subjects and occurrences)	Y			
Subject Numbers for Individual AEs				Y
Relationship Between AE SOC, Preferred Term & Verbatim Text				Y
Serious and Other Significant Adverse Events				
SAEs by SOC and Preferred Term (subjects and occurrences)	Y			
SAEs by Maximum Intensity	Y			
Reasons for Considering as a SAE				Y
Drug-Related SAEs by SOC and Preferred Term (subjects and occurrences)	Y			
Fatal SAEs by SOC and Preferred Term (subjects and occurrences)	Y			Y
Non-Fatal SAEs by SOC and Preferred Term (subjects and occurrences)	Y			Y
Drug-Related Fatal SAEs by SOC and Preferred Term (subjects and occurrences)	Y			
AEs Leading to Permanent Discontinuation of Randomized Treatment by SOC and Preferred Term	Y			Y
BP Exacerbation Events	Y			
BP Exacerbation SAEs	Y			
Other Significant AEs				Y
Other CV Events				
Other CV Events ²				

NOTES:

- T = Table, F = Figure, L = Listing, Y = Yes display generated.
- Summary = Represents TFL related to any summaries (i.e. descriptive statistics) of the observed raw data.
- Individual = Represents FL related to any displays of individual subject observed raw data.

[1]: Plot of common AEs and relative risk will be generated.

[2]: Electronically generated patient profiles will be produced and used in the preparation of SAE summaries as a part of the study report.

8.2.4.2. Planned Adverse Event Safety Statistical Analyses

AESIs & PhRMA SPERT Adverse Event Analyses

Adverse events of special interest are described in Section 10.6.4.

Summaries of AESIs will include the number, percentage and rate per 100 person-years of subjects having at least one occurrence, the number of events, the number of subjects by number of occurrence, the characteristics of the AE (serious, drug-related, etc.), outcome, maximum intensity, time to first onset/worsening, and action taken summarized by treatment group. For each count, a subject will be summarized as follows:

- **Serious/drug-related/severe/fatal:** If any specific AE falls in the respective category, the subject will be counted in that category.
- **Outcome:** The subject will be counted within a category if there is at least one specific AE in that category.
- **Maximum intensity:** The specific AE with the maximum intensity will be counted for this purpose. For example, a subject will be counted in the ‘severe’ category if there is at least one specific AE with severe intensity. A subject will be counted in the ‘moderate’ category if there is at least one specific AE with moderate intensity and there is no specific AE with severe intensity.
- **Time to first onset/worsening (days):** The earliest of onset dates for the specific AE – treatment start + 1

If the AE onset date/AE worsening and/or resolution date is missing or incomplete in the database for any occurrence of the specific AE, time to first onset/worsening will be left missing for the subject. These summaries of special interest AEs will be provided for those AEs classified as treatment emergent.

Cumulative incidence function (CIF) plots may be produced for each AESI summarizing the time to first occurrence of the AESI by treatment group. If there are less than 20 subjects total for both the daprodustat and darbepoetin alfa arm, then these plots will not be created. Competing risks for the AESI cumulative incidence plots include:

AE of Special Interest (Event of interest)	Competing Risk Events
Thrombosis and/or tissue ischemia secondary to excessive erythropoiesis	Death due to any cause prior to the AESI
Cardiomyopathy	Death due to any cause prior to the AESI
Pulmonary artery hypertension	Death due to any cause prior to the AESI
Cancer-related mortality and tumor progression and recurrence	All other non-cancer-related death prior to the AESI (use death date as the competing risk date)
Esophageal and gastric erosions	Death due to any cause prior to the AESI
Proliferative retinopathy, macular edema, choroidal neovascularization	Death due to any cause prior to the AESI
Exacerbation of rheumatoid arthritis	Death due to any cause prior to the AESI
Worsening of hypertension	Death due to any cause prior to the AESI

Additionally, as a part of the PhRMA SPERT analyses described in Section 8.2.4, treatment emergent AE of special interest are considered Tier 1 events. The relative risk, corresponding two-sided 95% confidence intervals and two-sided p-values comparing daprodustat vs. darbepoetin alfa for these Tier 1 AEs will be provided.

The number, percentage and rate per 100 person-years for subjects reporting Tier 2 AEs will be summarized by system organ class, preferred term and treatment group. Additionally, as a part of the PhRMA SPERT analyses described in Section 8.2.4, the most common treatment emergent AEs that are not Tier 1 AEs are considered to be Tier 2 AEs. The relative risk will be calculated for these Tier 2 AEs and a corresponding two-sided 95% confidence interval comparing daprodustat vs. darbepoetin alfa. Two two-sided p-values will be displayed: one that makes no adjustment for multiplicity and one that makes the double FDR adjustment.

Dot plots displaying the incidence of the event will be provided for the Tier 1 and Tier 2 events by AESI term (Tier 1)/ preferred term (Tier 2) and treatment group. The incidence rate in each treatment group and corresponding two-sided 95% confidence interval for the CMH relative risk of the daprodustat group compared to the darbepoetin alfa group will be provided.

Adverse Events

The number and percentage of subjects reporting at least one AE will be provided for each treatment group. These events will be summarized by treatment group, primary system organ class, and preferred term. Pre-treatment and treatment emergent AEs will be summarized separately.

The number and percentage of subjects and the number of occurrences of all treatment emergent AEs will be summarized by primary system organ class, and preferred term.

Summaries of all treatment emergent AEs will be produced for the age group, gender, race group, current ESA use at randomization, and weight quartile subgroups. Summaries of treatment emergent AEs by subgroup will be produced twice: by system organ class and preferred term and separately by overall frequency.

A listing of AE records for all subjects who reported AEs will be produced.

Summaries of all treatment emergent AEs will be provided by maximum intensity. For AEs reported more than once by a subject, the most severe intensity will be included in summaries where applicable. The max intensity will be presented as “Unknown” if Missing and/or N/A are the only available severity values. Analysis will be repeated for all drug-related treatment emergent AEs.

The number and percentage of subjects reporting the most common treatment emergent AEs (those occurring in $\geq 5\%$ of subjects in any treatment group) will be summarized by preferred term and treatment group.

The number and percentage of subjects reporting treatment emergent AEs assessed by the investigator to be related to the study drug will be summarized by treatment group, primary system organ class, and preferred term and separately by overall frequency.

The number and percentage of subjects and the number of occurrences of common non-serious treatment emergent adverse events (those occurring in $\geq 5\%$ of subjects in any treatment group) will be summarized by primary system organ class, preferred term and treatment group and separately by overall frequency.

A listing of which subjects reported specific adverse events will be produced.

The hierarchical relationship between MedDRA SOCs, PTs and verbatim text will be listed for all adverse events.

Serious and Other Significant Adverse Events

The number and percentage of subjects and the number of occurrences of treatment emergent SAEs will be provided for each treatment group. These events will be summarized by treatment group, primary system organ class, and preferred term. Treatment emergent SAE preferred terms will also be summarized by treatment group and overall frequency.

Summaries of treatment emergent SAEs will be provided by maximum intensity.

A listing of reasons for considering as a SAE will be produced for all treatment emergent SAEs.

The number and percentage of subjects and the number of occurrences of treatment emergent drug-related SAEs, fatal SAEs, non-fatal SAEs, and drug-related fatal SAEs will be summarized by treatment group: by primary system organ class and preferred term and separately by overall frequency.

A listing of treatment emergent fatal SAE records and a listing of treatment emergent non-fatal SAE records will be provided.

The number and percentage of subjects reporting treatment emergent AEs leading to discontinuation of randomized treatment will be summarized by treatment group, primary system organ class, and preferred term.

A listing of treatment emergent AEs leading to discontinuation of randomized treatment will be provided.

BP events and BP-related SAEs are defined in Section [10.6.4](#).

The number and percentage of subjects with at least one on-treatment BP event will be provided for each treatment group. In addition, this summary will include the number and percentage of subjects with at least one on-treatment BP event that is considered clinically significant and the number and percentage of subjects with at least one on-treatment BP event that is considered to be symptomatic.

The number and percentage of subjects reporting at least one treatment emergent BP-related SAE will be provided for each treatment group. In addition, the number of on-treatment BP-related SAEs will be summarized by treatment group, primary system organ class, and preferred term.

A listing of other significant adverse events will be produced. Other significant adverse events are events that are not reported as fatal or serious but represent ICH-defined ‘Other significant adverse events’ (i.e., marked haematological and other laboratory abnormalities and any adverse events that led to an intervention, including withdrawal of drug treatment, dose reduction, or significant additional concomitant therapy). For this study, other significant AEs will be defined as non-fatal non-serious AEs resulting in an action taken with study treatment of either ‘dose interrupted/delayed’ or ‘dose reduced’.

Other CV Events

GSK has identified other CV events of interest for all clinical studies. In this study, investigators will be required to fill out the specific CV event page of the eCRF for the following CV AEs and SAEs or any event that may potentially be one of the categories listed:

- Arrhythmias
- Pulmonary hypertension
- Valvulopathy
- Revascularization

Electronically generated patient profiles for subjects reporting these events will not be prospectively created.

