- If the last non-zero dose date is missing and the treatment start date is non-missing and the AE onset date or AE worsening date is on or after the treatment start date, then the AE will be considered to be treatment emergent.
- If AE onset date or AE worsening date is missing and AE resolution date is before the treatment start date, then the AE will be classified as Pre-treatment. If the AE resolution date is after the start of placebo run-in, the AE will also be considered a Placebo Run-in AE.
- If AE onset date or AE worsening date is missing and AE resolution date is either missing or on or after treatment start date, then the AE will be classified as treatment emergent and post-randomization.

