
 2. Order SOCs (small to large) according to the minimum FDR adjusted p-value observed for treatment differences across PTs within SOC. 3. Perform the FDR method on the minimum adjusted p-values from Step 2. 4. Select SOCs with FDR adjusted p-value from Step 3 <0.10. 5. Apply a single FDR adjustment to all unadjusted p-values belonging to all PTs from SOCs identified in Step 4. A threshold of FDR adjusted p-values <0.10 will be used to flag PTs that warrant further investigation. 
Note that 0.10 is recommended as a reasonable multiplicity adjustment for 0.05.

General Definitions

 • Post-Randomization last contact date for censoring (subjects not having AE) will be defined as the study completion date.

 • Treatment emergent last contact date for censoring (subjects not having AE) will be defined as follows: 
 ○ 1 day after the last non-zero dose date (last non-zero dose date + 1) for subjects not having treatment emergent AE and continuing on study past (last non-zero dose date + 1) ○ Last non-zero dose date for all other subjects

 • AE Patient Years: (Cumulative total of time to AE for subjects who have the AE + Cumulative total of censoring time for subjects without the AE) / 365.25 
 ○ For treatment emergent AEs, the start date of the patient years value for each subject should be the treatment start date. ○ For post-randomization AEs, the start date of the patient years value for each subject should be the randomization date. ○ For follow-up AEs, the start date of the patient years value for each subject should be 2 days after the last non-zero dose date (last non-zero dose date + 2).

 • Incidence Rate (per 100 patient years): $(100 * \text{Number of subjects with at least 1 AE}) / \text{AE person years}$

 • For the analysis of the time to AE onset/worsening, if the AE onset/worsening date is missing then the time to AE onset/worsening will be counted as 1 day.

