Adverse Events	
 ● The eCRF allows for the possibility of partial dates (i.e., only month and year or only year) to be recorded for AE start/worsening and end dates. In such a case, the following conventions will be applied for calculating the time to onset and the duration of the event: 
 ○ Imputing a Start/Worsening Date from a Partial Start/Worsening Date: 
 ○ If an imputed worsening date is before the start date, then the start date will be used as the imputed worsening date. ○ Completely missing stop date: 
 ➤ If only the day is missing, the first of the month will be used unless the Screen Week -8 visit date, Run-In visit date or treatment start date also occurs in the same month. 
 ● If the treatment start date occurs in the same month, then the treatment start date will be used as the start/worsening date. ● Otherwise, if the Run-In visit date occurs in the same month (and the treatment start date is not in that month), then the Run-In visit date will be used as the start/worsening date. ● Otherwise, if the Screen Week -8 visit date occurs in the same month (and the treatment start and Run-In visit dates are not in that month), then the Screen Week -8 visit date will be used as the start/worsening date. ➤ If the day and month are missing, then '01' will be used for the day and 'Jan' will be used for the month unless the Screen Week -8 visit date, Run-In visit date or treatment start date also occurs in the same year. 
 ● If the treatment start date occurs in the same year, then the treatment start date will be used as the start/worsening date. ● Otherwise, if the Run-In visit date occurs in the same year (and the treatment start date is not in that year), then the Run-In visit date will be used as the start/worsening date.

Element	Reporting Detail

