
Element	Reporting Detail
	
 ➤ If the day and month are missing, then '31' will be used for the day and 'Dec' will be used for the month, unless the stop date of study treatment also occurs in the same year; in this case the study treatment stop date will be used as the stop date. ○ Latest of (start date and latest worsening date) is partial or non-missing and is after treatment stop date: 
 ➤ If only the day is missing, the last day of the month will be used unless the study conclusion date also occurs in the same month; in this case, the study conclusion date will be used as the stop date. ➤ If the day and month are missing, then '31' will be used for the day and 'Dec' will be used for the month, unless the study conclusion date also occurs in the same year; in this case, the study conclusion date will be used as the stop date. ● Completely missing start, worsening or end dates will remain missing, with no imputation applied. Consequently, time to onset and duration of such events will be missing.
CV Safety Endpoint Events	Discussed in Section 10.6.4

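### Section 8.2.4.2 blanks the time to first AESI onset for gaps in dates the calculation does not need or that Section 10.7.2.1 imputes, and the SAP has two opposed rules for a completely missing onset date

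*SAP*

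**What the plan says.** Three places in the SAP govern the time to onset of an adverse event.

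- **Section 8.2.4.2** (AESI summaries) defines the quantity as "The earliest of onset dates for the specific AE – treatment start + 1". The paragraph after the list sets an exclusion, "If the AE onset date/AE worsening and/or resolution date is missing or incomplete in the database for any occurrence of the specific AE", with the consequence that "time to first onset/worsening will be left missing for the subject".
- **Section 10.6.4.4** (General Definitions) says, for the analysis of time to onset or worsening: "if the AE onset/worsening date is missing then the time to AE onset/worsening will be counted as 1 day".
- **Section 10.7.2.1** (missing and partial dates) says of partial adverse event dates that "the following conventions will be applied for calculating the time to onset and the duration of the event". For dates with nothing recorded it says: "Completely missing start, worsening or end dates will remain missing, with no imputation applied". It continues: "Consequently, time to onset and duration of such events will be missing".

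Section 10.4.1.4 is also relevant. "If AE onset date or AE worsening date is missing and AE resolution date is either missing or on or after treatment start date", the event is classed as treatment emergent. Events without an onset date therefore do reach the AESI tables, and a rule for them is needed.

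**The concern.** Time to first onset needs two dates: the earliest onset and the start of treatment. The exclusion in Section 8.2.4.2 adds a resolution date, which plays no part in the calculation, and it applies across all occurrences, so a gap in a later event removes a fully dated first one. It also treats a partial date as unusable, when another section of the same document imputes partial dates for this very calculation.

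The loss would not be random. Subjects with an unresolved event, or with several occurrences, are the likelier ones to have an incomplete date somewhere, so the onset-time row would lean towards subjects with single, resolved events. Separately, two programmers following Sections 10.6.4.4 and 10.7.2.1 would handle a completely missing onset date differently, and both would be following the plan.

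**Working it through.** The SAP states no figure to reproduce here. The check applies each rule to three constructed subjects. Treatment start is assumed to be 01JAN2018, and time = onset date − treatment start + 1, as in Section 8.2.4.2.

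**Subject 1.** First occurrence with onset 19FEB2018, resolved. Second occurrence with a complete onset date, ongoing, no resolution date.
- True value: 31 days of January + 19 = day 50.
- Section 8.2.4.2: missing, because one occurrence lacks a resolution date.
- Section 10.6.4.4: day 50, because no onset date is missing.
- Section 10.7.2.1: day 50. Its rules work event by event, and the first event is fully dated.

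**Subject 2.** One occurrence, onset recorded only as March 2018, complete stop date after treatment start.
- Section 8.2.4.2: missing, because the onset date is incomplete.
- Section 10.7.2.1: the first of the month is imputed, since treatment did not start in that month. That gives 01MAR2018, or 31 + 28 + 1 = day 60.

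**Subject 3.** One occurrence, onset completely missing, classed as treatment emergent under Section 10.4.1.4.
- Section 8.2.4.2: missing.
- Section 10.7.2.1: missing.
- Section 10.6.4.4: day 1.

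| Subject | 8.2.4.2 | 10.6.4.4 | 10.7.2.1 |
|---|---|---|---|
| 1 | missing | 50 | 50 |
| 2 | missing | no rule for partial dates | 60 |
| 3 | missing | 1 | missing |

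In each case at least two sections disagree. For subjects 1 and 2 the value lost under Section 8.2.4.2 is one that the rest of the SAP treats as known or imputable. Section 10.7.2.1 also has a branch for events whose stop date is completely missing, and that branch still imputes a partial onset. A missing stop date is therefore no obstacle there.

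**The case against.** The strongest reply is that little depends on this row. Section 8.2.4.2 blanks only the onset time. The subject still counts in the number and percentage with an event, the number of events, outcome, maximum intensity and action taken. The Tier 1 comparison in Section 8.2.4 uses the CMH test on the number and percentage of AESIs, with relative risks. No AESI p-value uses onset time. All of this stands and limits the point.

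A second reply is that the sections serve different purposes: Section 10.6.4.4, which also defines patient-years and censoring, would govern rates and time-to-event displays, and Section 8.2.4.2 only the descriptive row. That is a natural reading. It answers a stronger inference that a reader might draw, namely that the exclusion also removes subjects from AESI patient-years or from the cumulative incidence plots. The SAP does not say so, and the plots are in any case optional. But the SAP does not state the division either. It would not justify discarding known onsets in a descriptive row, and it leaves Sections 10.6.4.4 and 10.7.2.1 opposed.

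A third reply is that an ongoing event may not have a missing resolution date at all. Section 10.7.2 ties missingness to requested data that were not provided and exempts answers such as not applicable. The case report form is not shown, so this is possible. Section 10.4.1.4 does, however, speak of resolution dates as missing, and Section 8.2.4.2 exempts nothing. The conflict over partial dates does not depend on this.

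The resolution-date phrase may be left over from a duration item, such as the one in the parallel COVID-19 list in Section 8.2.9. That is inference, and it would make this a drafting slip rather than a deliberate choice. The text would still be programmed as written.

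**Conclusion.** The point holds as a defect of specification in a descriptive safety summary. Followed as written, Section 8.2.4.2 discards onset times that are known or that Section 10.7.2.1 imputes, and Sections 10.6.4.4 and 10.7.2.1 give opposite answers for a completely missing onset without saying which prevails.

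The size of the loss cannot be given. The SAP has no figure for ongoing or partly dated AESIs, so a claim that a large share of onset times would disappear is not supported. The loss for unresolved events also assumes that a blank resolution date on an ongoing event counts as missing, which is the literal reading but not a certain one. It would likewise be wrong to infer that unresolved AESIs drop out of the safety analysis: they leave one row only. The co-primary and principal secondary analyses are not involved.

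**What to change.** 1. In Section 8.2.4.2, delete the resolution date and the incomplete-date condition from the exclusion. Base time to first onset on the subject's earliest onset or worsening date, using the Section 10.7.2.1 imputation where that date is partial.
2. Reconcile Sections 8.2.4.2, 10.6.4.4 and 10.7.2.1 on a completely missing onset by naming the rule for each display. One workable split is 1 day for patient-years and cumulative incidence, so that no event is lost, and missing in the descriptive onset-time row. Using 1 day everywhere is not required and has a drawback: in the descriptive row it places unknown onsets at the start of treatment and pulls the distribution towards early onset.

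The cost is a few sentences in three sections and a small programming change. It is best made before unblinding.

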8.2.4. Adverse Event Safety Analyses

Adverse events will be coded using the Medical Dictionary for Regulatory Activities (MedDRA) coding dictionary.

The reporting of the CEC-adjudicated CV endpoint events has been described in Section 7.2, Section 8.2.1 and Section 8.2.2. However, AE summaries and analysis will also include the AEs and SAEs associated with the adjudicated events listed below:

- All-cause mortality (CV and non-CV mortality)
- Non-fatal MI
- Non-fatal stroke
- Hospitalization for HF
- Thromboembolic events (vascular access thrombosis, deep vein thrombosis, pulmonary embolism)
- Progression of CKD

For the purpose of AE summaries and analysis, the investigator-reported AE details will be used, regardless of the adjudication outcome of the event.

Adopting recommendations from the Pharmaceutical Research and Manufacturers of America (PhRMA) Safety Planning, Evaluation and Reporting Team (SPERT) [Crowe, 2009], the first two tiers of the three-tier system will be used for the evaluation of AEs to examine the level of statistical evidence for differences between treatment groups.

- Tier 1 events in this study are defined as treatment emergent AEs of special interest (AESI). Tier 1 events will include AEs which meet criteria for inclusion as an AESI (see Section 10.6.4). Statistical comparisons will be made to compare the number and % of AESIs between the treatment groups, using the CMH chi-square test. A nominal statistical association will be declared if the unadjusted two-sided p-value for an event is less than 0.05.
- Tier 2 events in this study are defined as the most common treatment emergent AEs (those occurring in $\geq 5\%$ of subjects in any treatment group). Tier 2 events are mutually exclusive of the Tier 1 AESI events. Any statistical comparisons for Tier 2 events will be made to compare treatment groups with multiplicity adjustment, using a CMH chi-square test, and the double false discovery rate (FDR, see Section 10.6.4) [Mehrotra, 2012]. The double FDR multiplicity procedure is designed to limit the number of false positive signals identified to no more than two-sided 10% (the false discovery rate).

Unless otherwise specified, all other AE and SAE summaries will include all AEs.

See Section 10.4.1 for AE treatment state definitions.

The adverse event safety analyses will be based on the Safety population, unless otherwise specified.

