10.4.1.4. Treatment States for AE Data

Non-serious AEs and serious AEs are to be recorded on the eCRF starting at the placebo run-in phase. Serious AEs assessed as related to study procedures or related to a GSK concomitant medication are to be recorded on the eCRF from the time a subject consents to participation in the study. AE of worsening of an on-going event will be counted once in a particular treatment state.

Treatment State	Definition
Pre-treatment	
 • For subjects with a non-missing screen failure date, if AE onset is on or before the screen failure date: AE Start Date \leq Screen Failure Date • For randomized subjects with a missing treatment start date, all AEs are considered pre-treatment • For randomized subjects with a non-missing treatment start date, if AE onset date is before treatment start date: AE Start Date $<$ Treatment Start Date
Placebo Run-In	
If AE onset date or AE worsening date is on or after placebo run-in treatment start date & on or before placebo run-in treatment stop date: Placebo Run-in Treatment Start Date \leq AE Start Date \leq Placebo Run-in Treatment Stop Date Placebo Run-in Treatment Start Date \leq AE Worsening Date \leq Placebo Run-in Treatment Stop Date AE worsening during placebo run-in will be defined relative to the maximum intensity of AE prior to placebo run-in start date. AE worsening date is the first date in the placebo run-in period, when AE intensity increased relative to the maximum intensity of the AE prior to placebo run-in start date.

Post-randomization	
If AE onset date or AE worsening date is on or after the randomization date Randomization date \leq AE Start Date Randomization date \leq AE Worsening Date AE worsening during post-randomization will be defined relative to the maximum intensity of AE prior to randomization date. AE worsening date is the first date in the post-randomization period, when AE intensity increased relative to the maximum intensity of the AE prior to randomization date.

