Treatment emergent	
If AE onset date or AE worsening date is on or after treatment start date & on or before the last non-zero dose date plus 1 day. Treatment Start Date \leq AE Start Date \leq Last Non-Zero Dose Date + 1 day Treatment Start Date \leq AE Worsening Date \leq Last Non-Zero Dose Date + 1 day AE worsening during treatment emergent will be defined relative to the maximum intensity of AE prior to randomized treatment start date. AE worsening date is the first date in the treatment emergent period, when AE intensity increased relative to the maximum intensity of the AE prior to randomized treatment start date.

Follow-up	
If AE onset date or AE worsening date is after the last non-zero dose date plus 1 day. AE Start Date $>$ Last Non-Zero Dose Date + 1 day AE Worsening Date $>$ Last Non-Zero Dose Date + 1 day AE worsening during follow-up will be defined relative to the maximum intensity of AE prior to randomized treatment start date. AE worsening date is the first date in the follow-up period, when AE intensity increased

	relative to the maximum intensity of the AE prior to randomized treatment start date.
Onset /Worsening Time Since 1 st Dose (Days)	If Treatment Start Date > AE Onset Date = AE Onset Date - Treatment Start Date If Treatment Start Date ≤ AE Onset Date = AE Onset Date - Treatment Start Date + 1 If Treatment Start Date > AE Worsening Date = AE Worsening Date - Treatment Start Date If Treatment Start Date ≤ AE Worsening Date = AE Worsening Date - Treatment Start Date + 1 Missing otherwise.
Onset/Worsening Time Since Last Dose (Days)	If Last Non-Zero Dose Date ≤ AE onset date: AE onset date – last non-zero dose date +1 If Last Non-Zero Dose Date > AE onset date: AE onset date – last non-zero dose date If Last Non-Zero Dose Date ≤ AE worsening date: AE worsening date – last non-zero dose date +1 If Last Non-Zero Dose Date > AE worsening date: AE worsening date – last non-zero dose date Missing otherwise.
Duration (Days)	AE Resolution Date – AE Onset Date/AE Worsening Date + 1
Drug-related	If relationship is marked 'YES' on eCRF or if the value is missing.

NOTES:

- AEs that occur or worsen during interruptions of randomized study treatment will be classified as treatment emergent and post-randomization.

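### The cancer AESI is compared between arms only up to one day after the last dose, although AESIs are collected to End of Study; add a post-randomization result beside it

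*SAP*

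**What the plan says.** Section 8.2.4 restricts Tier 1 to treatment-emergent AESIs and sets the test: "Statistical comparisons will be made to compare the number and % of AESIs between the treatment groups, using the CMH chi-square test". Section 8.2.4.2 attaches the relative risk, confidence interval and p-value to those Tier 1 events. It limits the AESI tables in the same way: "These summaries of special interest AEs will be provided for those AEs classified as treatment emergent". Tier 2 excludes AESIs, so cancer is not tested there either.

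Section 10.4.1.4 requires onset or worsening "on or before the last non-zero dose date plus 1 day". It adds one inclusive rule: "AEs that occur or worsen during interruptions of randomized study treatment will be classified as treatment emergent and post-randomization". Section 10.6.4.4 lists cancer death, progression and recurrence as one AESI, with no window of its own.

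The schedule in Section 10.2.1.3 nevertheless collects AESIs from subjects who have permanently stopped treatment, at scheduled visits and at End of Study. Section 10.4.1.4 also defines a post-randomization state, with the condition "If AE onset date or AE worsening date is on or after the randomization date". Section 10.6.4.4 supplies its patient-years and censoring. No AESI table or test in Section 8.2.4 is specified on that state.

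**The concern.** Two things are at stake for a safety concern that the sponsor named in advance.

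First, a cancer whose onset or worsening falls more than one day after the last dose is left out of the only between-arm cancer comparison, whether fatal or not. The plan treats cancer death as part of this AESI: in the competing-risk table of Section 8.2.4.2, the cancer row alone counts only deaths from other causes as competing. A fatal cancer that began off treatment still enters no AESI comparison.

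Second, the tested quantity is a number and a percentage, which rise with time on treatment. In an open-label trial that time may differ between arms. The definition adds an asymmetry of its own. Section 10.6.1 takes the last date on which a dose was actually taken. Daprodustat is daily, while several darbepoetin dose steps in Section 10.6.3.6 are given every 4 weeks. A darbepoetin subject who stops just before the next injection loses nearly four weeks of window; a daprodustat subject does not.

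**Working it through.** **No figure to reproduce.** The SAP states no cancer rate, discontinuation rate or power for this comparison. The only documented input is N = 4500 randomized 1:1 (Section 2.3), so n = 2250 per arm. Every other input below is assumed.

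**1. Events left out and power.** Assume 3.0% of one arm has a cancer AESI by study end and an on-treatment relative risk of 1.50. Let *s* be the share of the 3.0% arm's events that start off treatment. With event counts *a* and *b*:

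SE(log RR) = √(1/a − 1/n + 1/b − 1/n); power = Φ(ln RR / SE − 1.96).

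The 3.0% arm has 2250 × 0.030 = 67.5 events in all.

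| | s = 20% | s = 30% | s = 40% |
|---|---|---|---|
| 3.0% arm's events left out (67.5 × s) | 13.5 | 20.25 | 27 |
| **Treatment emergent:** events | 81 / 54 | 70.9 / 47.25 | 60.75 / 40.5 |
| RR (95% CI) | 1.50 (1.07–2.11) | 1.50 (1.04–2.16) | 1.50 (1.01–2.22) |
| Power | 0.649 | 0.590 | 0.524 |
| **Post-randomization, harm persists:** events | 101.25 / 67.5 | same | same |
| RR (95% CI) | 1.50 (1.11–2.03) | same | same |
| Power | 0.748 | same | same |
| **Post-randomization, no off-treatment effect:** events | 94.5 / 67.5 | 91.1 / 67.5 | 87.75 / 67.5 |
| RR (95% CI) | 1.40 (1.03–1.90) | 1.35 (0.99–1.84) | 1.30 (0.95–1.78) |
| Power | 0.575 | 0.477 | 0.378 |

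In the last block the higher-risk arm's proportion is 0.045(1 − s) + 0.030s. Replacing 0.030s by 0.030s·r and solving for the off-treatment relative risk r that gives equal power yields r = 1.20, 1.19 and 1.18. Above about 1.2 the post-randomization analysis has more power; below it, the treatment-emergent analysis does.

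**2. Dependence on treatment time with no true difference.** Take a constant cancer hazard h = 0.02 per year, F = 2 years of follow-up, and on-treatment shares s₁ and s₀ of that follow-up:

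RR of percentages = (1 − e^(−hFs₁)) / (1 − e^(−hFs₀)).

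- 0.80 versus 0.75: 1.066
- 0.80 versus 0.70: 1.141

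Over h = 0.01 to 0.03 and F = 2 to 3 years, the ranges are 1.064–1.066 and 1.138–1.142. The post-randomization relative risk stays at 1.0. The treatment-emergent rate ratio also stays at 1.0, because its person-time ends with the same window.

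The direction depends on which arm stops more. With constant discontinuation hazards d, the on-treatment percentage is h/(h + d) × (1 − e^(−(h+d)F)). At h = 0.02, d = 0.25 versus 0.20 per year gives RR 0.96 at 2 years and 0.94 at 3 years; d = 0.30 versus 0.20 gives 0.91 and 0.88.

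**3. Follow-up time outside the window.** The share of follow-up after the last dose is 1 − (1 − e^(−dF))/(dF). For d = 0.10 to 0.30 per year and F = 1.5 to 3 years it runs from 7% to 34%.

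**The case against.** The strongest reply is that nothing here is an error. The treatment-emergent window is explicit, conventional and applied alike to all eight AESIs, and the comparison is nominal and unadjusted. Collection is complete: late cancers are in the AE listing, and off-treatment cancer deaths appear by cause of death (Section 8.2.2.2) over the vital-status period (Section 10.6.4.1). The IDMC also sees serious adverse events while the trial runs. The AESI tables already give a rate: "Summaries of AESIs will include the number, percentage and rate per 100 person-years of subjects having at least one occurrence". The added analysis is not clearly better either. It includes time off treatment and time on later non-randomized ESA, the comparator's class, and loses power if the harm stops with the drug. All the sizes are assumed.

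Much of this stands. The treatment-emergent analysis is legitimate, the gap is mainly non-fatal cancers arising after permanent discontinuation, and power alone does not favour the addition. But listings, cause-of-death counts and IDMC reports give no between-arm comparison of off-treatment cancers. The planned rate is reported by arm with no between-arm estimate stated, so it does not protect the tested count and percentage from differences in time on treatment. The optional cumulative incidence plot states no window and carries no test.

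**Conclusion.** The point holds as a cheap improvement, not as an error in the primary analysis. The cancer AESI summaries and their only formal comparison omit events that start or worsen after last non-zero dose + 1 day, although the data are collected and the definitions needed to count them exist.

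Under the assumed 3.0% incidence and 20 to 40% off-treatment share, that is about 14 to 27 of 67.5 events in one arm. Under the assumed differences in treatment time, the tested relative risk moves from 1.0 to 1.07–1.14 with no true effect, or below 1.0 if the imbalance runs the other way. The actual size cannot be known from the SAP.

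The gain is a comparison that covers all collected cancers and does not depend on treatment duration. A gain in power follows only if the off-treatment relative risk exceeds about 1.2. Neither analysis dominates, so both should be shown. Cancers with on-treatment onset, and events during treatment interruptions, are already counted.

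**What to change.** Keep the treatment-emergent AESI results unchanged. In Section 8.2.4.2 add, for the cancer AESI only, the number and percentage of subjects, the rate per 100 patient-years, and the CMH relative risk with 95% CI. Base them on the post-randomization state of Section 10.4.1.4 and the patient-years and censoring of Section 10.6.4.4. Fix this before unblinding, so that the window is not chosen after the results are seen.

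The cost is one sentence and one repeated display, with no new data or definitions. The drawback is dilution by off-treatment and later ESA time when a harm does not persist. For that reason the result belongs beside the treatment-emergent one and should not replace it.
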